1) Human Subjects Involvement and Characteristics: Patients with documented IGR will be entered in the study. All patients will have baseline HbA1c measurements between <8%. All participants will have mild neuropathy as described below. A total of 142 participants will be entered in equal proportions between the two groups (SC and TDPA) using a minimization procedure. The scheme will be prepared to achieve equal sample sizes for the two groups, for age, gender, BMI, time from diagnosis of IGR. Persons assessing diet, PA, mobility function and neuropathy progression will be blinded to group assignment.

This research topic is relevant to both women and men, and both will be included as they are recruited, approximately in proportion to their representation among older adults with T2DM. African-Americans will be recruited in proportion to their numbers among patients with T2DM, and if needed, emphasis on recruiting African-Americans will assure they are not underrepresented in the study. Other minorities will be recruited based on their percentage in Washtenaw County, the primary recruitment region (3% Asian American, and 2% Hispanic).

Table 6 indicates the distribution of patients in Baltimore County, Maryland where the Baltimore VAMC and the University of Maryland are located and in Washtenaw county where the Ann Arbor VAMC and University of Michigan Hospitals are located. The distribution of Black or African Americans in Baltimore county is twice the national average and in Baltimore is over five times the national average thus increasing recruitment of minorities from this population group. In contrast, the distribution of Asian/Pacific Islander and Native American or Alaskan Native is greater in Washtenaw county than in Baltimore, increasing recruitment of these population group in Michigan. Both site will relatively under recruit Hispanics, although the rate of growth of this group is now among the highest in the nation in the greater Baltimore area. The distribution of patients seen at the Baltimore VAMC and the Ann Arbor VAMC is similar to respective demographics listed below with the exception that the proportion of male to female patients is greater. T2DM is more common in blacks than in the general population, and as much as three times more prevalent in some groups of American Indians (20), thus we predict that we will recruit an increased number of minorities into the study.

Table. 6: Baltimore (Baltimore VAMC and University of Maryland) and Washtenaw County (Ann Arbor VAMC and University of Michigan) Hospital Demographics

MARYLAND/BALTIMORE COUNTY HOSPITAL DEMOGRAPHICS (%s)							
	American Indian / Alaskan Native	Asian or Pacific Islander	Black, not of Hispanic Origin	Hispanic of any race	White, not of Hispanic Origin	Other or Unknown	* TOTAL
Female	0.054	2.11	12.96	1.35	37.48	1.24	55.19 (52)
Male	0.046	1.79	11.04	1.15	32.12	1.06	47.21 (48)
Unknown	0.0	0.0	0.0	0.0	0.0	0.0	0.0
Total	0.1	3.90	24.0	2.50	69.60	2.30	102.40 (100)

DATA SOURCE: **Baltimore County**; US Census Bureau, Census 2005. & Census 2005 Brief – Overview of Race and Hispanic Origin

CITY OF BALTIMORE HOSPITAL DEMOGRAPHICS (%s)							
	American Indian / Alaskan Native	Asian or Pacific Islander	Black, not of Hispanic Origin	Hispanic of any race	White, not of Hispanic Origin	Other or Unknown	* TOTAL
Female	0.23	0.93	37.32	1.32	17.37	1.50	58.67 (54)
Male	0.17	0.68	27.88	0.98	12.84	1.10	43.65 (46)
Unknown	0.0	0.00	0.0	0.0	0.0	0.0	0.0
Total	0.4	1.60	65.20	2.30	30.20	2.60	102.32 (100)

DATA SOURCE: **Baltimore Metropolitan Area**; US Census Bureau, Census 2005. & Census 2005 Brief – Overview of Race and Hispanic Origin

WASHTENAW COUNTY (MICHIGAN) HOSPITAL DEMOGRAPHICS (%s)							
	American Indian / Alaskan Native	Asian or Pacific Islander	Black, not of Hispanic Origin	Hispanic	White, not of Hispanic Origin	Other or Unknown	* TOTAL
Female	0.18	3.17	6.15	1.37	38.70	1.81	51.37 (50)
Male	0.18	3.17	6.15	1.37	38.70	1.81	51.37 (50)
Unknown	0.0	0.0	0.0	0.0	0.0	0.0	0.0
Total	0.36	6.34	12.29	2.74	77.40	3.61	102.74 (100)

DATA SOURCE: **Washtenaw County**; US Census Bureau, Census 2000. & Census 2000 Brief – Overview of Race and Hispanic Origin

Sources of Materials

The majority of data collected will be directly from the human subject and will include basic demographic data, a patient history, physical examination, NCS. Assessments of PA and mobility function will be performed as indicated in the protocol. Clinical surveys include the MDNS. In addition, we will obtain:

- 1) 100 mls of blood from subjects to perform biochemical measures of metabolic function, genetic, and proteomic studies at enrollment, at 6 months, and at 12 month follow up visits.
- 2) Three 3 mm skin punch biopsies will be performed on the left thigh and calf at enrollment and 12 months.

We will also request to corroborate the subject interview with inspection of their medical records that may include information about their number of physician visits and hospitalizations related to T2DM. All HIPAA requirements will be carefully followed.

Potential Risks

The risks to the subjects from participation in this study are low and consist predominantly of any adverse effects consequent to a tailored diet and physical activity program. There are no significant risks to the patient from NCS, which are used in routine clinical practice. Patients may have mild discomfort during the NCS.

In the IGTN study, there were no significant complications from the skin biopsy with the exception of minor bleeding. There is a risk from bleeding in participants taking blood thinning medications such as coumadin. There is a remote risk of skin infection at the site of the skin biopsy, although this did not occur in the IGTN study. In the current IGTN study, use of NSAID has not been a contraindication to performing a biopsy. **There is also a risk of keloid formation, delayed healing, or scarring.**

There is a risk of worsening clinical angina, arrhythmias, myocardial infarction, and pulmonary symptoms and of possibly provoking death when an exercise program does not involve proper screening and monitoring. Given the known comorbidities and complications associated with T2DM, participants may have a number of symptoms related to the exercise program, such as localized muscle pain, joint pain, or cramping with soreness, sensations of warmth, sweating, fatigue, loss of balance, light-headedness, dizziness, irregular heart beat, chest pain, or shortness of breath. Some of these symptoms may be related to hypoglycemia. These risks are all research risks, given that the training measures, although commonly used, are part of a research paradigm.

Adequacy of Protection from Risks

1) Recruitment and Informed Consent: 128 subjects (64 per subject group) will be recruited. Using the actual 1 year drop out for enrolled subjects from the IGTN study of <4%, the number of subjects to be enrolled is 133 and 142 if we assume a more liberal dropout of 10%. This requires that we recruit 6-7 patients/month for 21 months. A recruitment plan is outlined in the recruitment section of the grant. A flyer has been designed (subject to Human Use approval) to provide information about the program. After showing interest, a potential participant will be contacted by telephone **or email** by trained study personnel to begin to determine eligibility. An appointment at their convenience will be made and the project will be further explained together with the subjects review of the consent form, which will be signed, if the subject wishes to participate in the study. The consent form will be a written document that is fully in compliance with the requirements of the Veterans Administration Human Studies Committee. The consent will be obtained by the study coordinator or study physician. The nature of the information provided to subjects (which will be included on the consent document, a copy of which will be kept by the subject) will include a description of the background of the study, the relevance and purpose of the study, and a detailed description of the type of procedures that the patient will undergo including any potential risks or discomfort that will be experienced. The potential long-term benefits of any new data derived will also be explained as will any direct utility to the

individual concerned. Confidentiality will be ensured as all data will be kept in a locked cabinet within a locked office. Only named investigators on the Human Studies application will be aware of the patient's identity and clinical details. The patient may withdraw from the study at any time.

2) Protection Against Risk: In order to minimize any potential possibility for risk, women of childbearing potential must be using an acceptable method of contraception to prevent pregnancy when they are enrolled in the study and must agree to continue to practice an acceptable method of contraception for the duration of their participation in the study. Subjects will have the potential side effects explained to them. In order to perform blood samples for metabolic function, a small cannula will be placed into a vein of the arm in order to draw blood samples that involve a small amount of discomfort. We will aim to collect approximately 40 mls of blood (6 teaspoons) at each time point for metabolic studies.

There are no significant risks to the patient from NCS. NCS are used in routine clinical examination. Patients will be warned of mild discomfort during the NCS.

Skin biopsies will not be performed in subjects on anticoagulants or with poor skin condition. To avoid infection post skin biopsy, the procedure is performed under sterile conditions, antiseptic ointment is applied to the biopsy site and bandaged with sterile dressings. Participants are warned to keep the biopsy site dry for 72 h, and to replace the dressings with antiseptic ointment and bandages provided by the study team. **Skin biopsies are performed as a routine clinical procedure at the Maryland and Michigan sites and in over 200 patients have not been associated with any adverse effect.**

The entry criteria for the study exclude potential participants with other significant medical illness such as angina or pulmonary disease, and based on the IGTN study no participant has had a medical reason why they cannot exercise. Potential participants with other conditions such as joint disease, amputations etc. that would limit exercise are excluded from the study.

The protocols for testing and training have been chosen to minimize risk, and we believe that there are no other alternatives that would provide the information we seek while reducing risk further. We have minimized these risks by using careful screening and monitoring, and with careful instructions to our participants. Data (including our own) exists showing that it is safe for older adults with chronic disease and functional impairment to participate in both on-site and home exercise programs.

Confidentiality will be maintained to the fullest extent possible. The data will be entered into an access protected electronic database, each subject will be coded and personal identifiers will be removed, and paper copies of all original documents will be maintained in the study binder. Longstanding protocols have been in place, including data coding by subject number, locked in file cabinets, and cross-referenced by a name-number key in another location. Biological specimens will be coded and stored in a locked refrigerator in a locked room as already established for current VAMC studies.

3) Independent Safety and Data Monitoring Committee: This study will use a lifestyle intervention, and it is not predicted from the IGTV study that a standing independent SDMC will be required. All serious adverse events (SAEs) will be reported to the University of Maryland Institutional Review Board (UMIRB), which oversees both University of Maryland and Baltimore VA clinical research studies, or the Ann Arbor Human Studies Subcommittee (AAHSS) at their monthly meetings. If in the opinion of the IRB or the HSS, the number of probably related SAEs is determined to be higher than predicted, then an SDMC will be convened under the direction of **[name], the Chair of Neurology at the University of Maryland**. The records for the study will be reviewed, and a preliminary data analysis and assessment of frequency of SAEs and AEs will be performed with the assistance of the study statistician, [name]. A report of the SDMC findings, recommendations, and study requirements will be submitted to the UMIRB, the AAHSS, and the study investigators, and compliance will be overseen by the SDMC, the UMIRB, and the AAHSS.

Potential Benefit of the Proposed Research to the Subject and Others

There may be no or only minimal benefit to the subject from participation in this study. This will be indicated in the informed consent. Early peripheral neuropathy may result in severe neuropathic pain. Potentially the TDPA program may affect the participants response or perception of pain.

The exercise and diet program may improve general health, fitness, and overall well-being. All subjects will receive some instruction regarding exercise and diet, although the benefits may vary in type and amount, which is part of the research question. The screening evaluation may be useful for the participants and if permitted by the participants, to their physicians, due to the thorough evaluation and stress testing.

Importance of the Knowledge to be Gained

Knowledge will help determine if a TDPA program is able to prevent, or ameliorate neuropathy in persons with IGR and improve function and mobility. There is currently no effective treatment for diabetic neuropathy, other than improved glycemia. Thus any improved therapy that helps to prevent one of the most severe and costly complications of diabetes, namely diabetic neuropathy, would provide significant benefit within the population. New knowledge related to the treatment and mechanism of neuropathy outweigh the small risks from the tests performed and the TDPA intervention.

In summary, important potential benefits exist for the participants, including improved fitness and possible well-being and useful medical information. In addition, extremely useful information with potential to benefit other older adults with diabetes will be obtained. Given the extensive plan to minimize risk, the risk: benefit ratio appears acceptable.

Expertise of the PIs in this Project

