This study will use a lifestyle intervention and it is not predicted from the current IGTN study that a standing independent SDMC will be required. If necessary, a plan for convening a SDMC is described in Human Studies (see Appendix).

General analytic plan

Comparability of treatment groups will be performed using the baseline demographic variables (i.e. age, gender, BMI) and relevant prognostic covariants (e.g., HbA1c, autonomic symptoms, and baseline values of primary endpoints). The demographic and prognostic values will be presented by treatment group as means and standard deviations for continuous variables, and analysis of variance will be used to compare the means of the two treatment groups, controlling for baseline. Baseline characteristics will be compared between the study groups. Standard two group comparison methods will be used, such as two sample t-tests for normally distributed variables. Measures of central tendency (means) and variability (standard deviations, ranges) will be estimated. Initial data analyses will allow us to explore the distributions of outcomes studied, may lead to transformation of the dependent variable, and may help identify outlying measures not detected earlier in the data cleaning process.

1) Model check and alternative analysis plans: Model fits will be checked for individual and systematic departures of the observed and fitted values using informal (e.g. inspection of residuals) and formal methods (e.g. based on score tests for extra parameters (104;105). The influence of individual outliers will be evaluated by comparing models with and without outlying values. Outcome variables will be transformed when we cannot fit a parametric model. In our

preliminary data, assumption of normality is reasonable for most outcome variables, including those which are log transformed. Non-parametric analyses e.g. Generalized Additive Models (GAM), (106), or Friedman two-way analysis of variance (105), will be utilized when we cannot fit a parametric model. Outcome measures will be adjusted for baseline by including baseline values as a covariate into the model. As another option, a baseline measure becomes another dependent variable in the repeated measures model and appropriate contrasts will be constructed to adjust for baseline. In computations, SAS PROC MIXED (107), SAS PROC GENMOD, and PROC GAM in SPLUS will be used.

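### SAEs are to be reported at the boards' monthly meetings and no faster route is given, so the first outside notice of a serious event can lag by up to about a month

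*Combined protocol and SAP*

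**What the plan says.** The reporting rule is in item 3, Independent Safety and Data Monitoring Committee, under Adequacy of Protection from Risks. It opens "All serious adverse events (SAEs) will be reported to the University of Maryland Institutional Review Board (UMIRB" and, after noting which studies that board oversees, names the Ann Arbor subcommittee as the alternative recipient, with the reports made "at their monthly meetings". It covers every SAE. It sets no separate timeline for fatal, life-threatening or intervention-related events.

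The same item explains why no standing committee is planned: "it is not predicted from the IGTV study that a standing independent SDMC will be required". The shorter paragraph on the committee, just before the General analytic plan, says likewise that "it is not predicted from the current IGTN study that a standing independent SDMC will be required". A committee is convened only if a board judges that probably related SAEs outnumber what was predicted.

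The Potential Risks section calls participants' risks low. It also states: "There is a risk of worsening clinical angina, arrhythmias, myocardial infarction, and pulmonary symptoms and of possibly provoking death". That sentence ends by limiting the statement to exercise programs without proper screening and monitoring. The section then lists chest pain and irregular heartbeat among possible exercise symptoms, without that limit.

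On accrual, Recruitment and Informed Consent says: "This requires that we recruit 6-7 patients/month for 21 months".

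**The concern.** A monthly meeting suits cumulative review, but it is a slow channel for first notice of a serious event. Here it is the only channel to anyone outside the study team for which a time is stated. TDPA participants exercise at home, and people keep entering the program while an event waits for the next meeting. If an event showed that screening or monitoring needed attention, the boards would learn of it only after others had started under the same arrangements.

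The rule also sends each SAE to one board or the other. Nothing in the text passes a new SAE to the second site. Findings reach both boards only through a committee report, if a committee is ever convened.

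**Working it through.** **Inputs**

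- Reporting interval: monthly, taken as about 30 days (committee item under Adequacy of Protection from Risks).
- Participants entered: 142, in equal proportions to the two groups (Human Subjects Involvement and Characteristics).
- Recruitment period: 21 months at 6-7 per month (Recruitment and Informed Consent).
- Program length: 12 months (TDPA Behavioral Component).
- SAE rate: not given.

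**Step 1. Reproduce the plan's accrual figure.** 142 / 21 = 6.76 per month, which agrees with the stated 6-7. In the other direction, 6 × 21 = 126 and 7 × 21 = 147, a range that contains 142.

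**Step 2. Delay to first outside notice.** The wait from an SAE to the next meeting runs from 0 to about 30 days. If SAEs fall evenly over the interval, the mean is 30 / 2 = 15 days. This assumes that the team learns of the event at once. Scheduled exercise contact is weekly in months 0-3, every two weeks in months 4-6 and monthly in months 7-12, so a late-learned event adds to the wait.

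**Step 3. New TDPA starts during a wait.** With equal allocation, 6.76 / 2 = 3.38, or about 3.4 starts in a full month (3.0 to 3.5 at 6-7 per month). Over the mean wait of half a month the figure is 3.38 / 2 = 1.7.

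**Step 4. Participants in the program at once.** Each stays for 12 months, so the maximum at steady accrual is 3.38 × 12 = 40.6, about 41 (36 to 42 at 3.0 to 3.5 starts per month). This ignores dropout and so is an upper figure. The whole TDPA arm is 142 / 2 = 71, but those 71 are not in the program together.

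**Step 5. Look for another outside route.** Protection Against Risk provides physician supervision, evaluation of injuries by study staff and telephone contact that asks about problems. It also provides quick notice to the participant's own physician or nurse practitioner, if the participant agrees. The first three are internal to the study, and the last concerns the individual's care. None brings the event before an outside reviewer of the trial.

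**The case against.** **The sentence may not set a reporting time.** It could describe where the boards consider SAEs, or the monthly phrase could attach to Ann Arbor alone. Nothing forbids staff from reporting sooner. These readings are possible but less natural: the verb is about reporting, and the plural possessive fits both boards. If only Ann Arbor is meant, Maryland has no stated timing at all, and the sentence still needs correcting.

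**The boards may have faster rules of their own.** They may, and then the delay would be largely a matter of drafting. The text cites no such rules. It also omits some pages and refers to appendices that are not reproduced, so the absence of a faster route is shown only for the text available. This part of the objection stands as a limit.

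**The risk is low and participants are not unmonitored.** This largely stands. A reader might infer that the protocol expects heart attacks or deaths in this program. It does not: it ties them to programs that lack proper screening and monitoring, and it excludes advanced ischemic heart disease and severe pulmonary disease. Chest pain and irregular heartbeat are still listed as possible symptoms, so a serious cardiac event is not ruled out.

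**No standing committee is a reasoned choice.** A reader might take its absence as the defect. The documents give a rationale (a lifestyle intervention and the experience of the earlier cohort) and a way to convene one. The absence matters here only because it leaves the boards as the sole standing outside check.

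**The exposure can be overstated.** A reader might add about 3 new starts to the 71 assigned to TDPA. That cannot happen, because 71 is the full arm and recruitment ends when it is filled.

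**Conclusion.** The point holds as a defect in a stated timing rule. Read in its ordinary sense, the plan lets first outside notice of any SAE come 0 to about 30 days after the event, with a mean near 15 days if events are evenly spread and the team learns of them at once. During recruitment, a full month's wait covers about 3.4 new TDPA starts, with at most about 41 participants in the program.

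The conclusion rests on three conditions: meetings about 30 days apart, steady accrual at the planned rate, and no quicker board rule in material outside the text reviewed. Without an SAE rate, neither the number of delayed reports nor any resulting harm can be estimated. Earlier reporting would bring earlier notice, but how soon a board would act on it cannot be judged from the documents. The correction is worth making because it is cheap and bears on safety. The documents do not show that participants are being put at high risk.

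**What to change.** In the committee item under Adequacy of Protection from Risks, replace the timing phrase so that the rule reads:

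> Each SAE is reported to the responsible board (UMIRB or AAHSS) when the study team becomes aware of it, without waiting for the next monthly meeting, and is copied to the investigators at the other site; the monthly meeting receives a cumulative summary.

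If either board already has its own reporting timeline, cite it in the same place.

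The cost is one sentence in the protocol and a little more paperwork per SAE. Endpoints, sample size, the intervention and the decision not to have a standing committee are unaffected.
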